## Interventions and Interactions

### Evaluation Schedule Summary:

Evaluation	History / Pre-Op	Intra-Op	1 day	4 days	1 week	30 days ± 7 days	3 months ± 2 weeks	6 months ± 2 weeks	1 year ± 1 month
Patient • IKDC demographics	X								
• IKDC current health	X							X	X
• IKDC subjective knee evaluation	X					X	X	X	X
Patient phone calls • Pain scores/pain medication log			X	X					
Physician • IKDC knee history	X								
• IKDC surgical documentation form		X							
• IKDC knee examination form	X					X	X	X	X
• Document rehab duration						X	X		
Stitch Removal/ Postop Follow-up for Pain/Meds					X				

The study will include six visits: one pre-surgery visit and five post-surgery visits at one week, 30 days, three months, six months, and one year. The one week, 30 day, and three month follow-up visits coincide with the standard of care follow-up visits for patients who undergo knee arthroscopy. The six month and one year visits will be for research purposes and will not be billed to insurance providers.

Additionally, the patients will be contacted by phone at 1 and 4 days after surgery to determine their visual analog pain scores and their use of pain medications. Patients will also keep a daily log of their pain level and use of pain medications. These calls will also be used to remind patients to complete their pain diaries.

*Randomization:* A blocked randomization scheme (block size of 10) will be used to assign study participants to either single portal (Group 1) or two portals (Group 2) knee arthroscopy. Prior to surgery, the surgeon will log on to the randomization website to determine each participant's surgical group assignment. After randomization for each patient is complete, the website will document the name of the person who logged on to perform the randomization, the date and time of the log in, and the surgical group assignment for each patient. In addition, the website will document the patient's name, medical record number, and study treatment allocation. This randomization information will be forwarded to the operating room staff so that they can prepare for each study participant's surgical procedure.

If during the surgical procedure, a patient who was randomized to the single portal technique is found to require a two portal technique, this patient will be recorded as a treatment cross-over as long as the patient continues to meet inclusion criteria. This will also be true for patients randomized to the two portal technique who undergo the single portal technique. Cross-over patients will not be excluded from the study. We are anticipating that only a small number of patients will be cross-over patients.

*Surgery:* Patients in Group 1 will undergo knee arthroscopy using a single portal. Patients in Group 2 will undergo knee arthroscopy using two portals. The details of the surgical procedure for each study participant will be documented on the IKDC Surgical Documentation Form.

*Post-surgical follow-up:* Study participants in each group will return for standard post-operative follow-up visits at one week, 30 days, and three months. They will return to the clinic at six months and one year for study visits. These two visits will not be billed to insurance providers.

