### **Sample Size:**

Power calculations were performed based on data from previous studies. Van de Graaf found a standard error of the mean (SEM) of 5.3 and a smallest detectable difference (SDD) of 14.6 for the Subjective Knee Evaluation Form part of the International Knee Documentation Committee (IKDC).(2) These measures were slightly larger than the SEM of 4.6 and the SDD of 9.0 reported by Irrgang.(1) Based on these values, power calculations identified the desired sample size as 50 patients in each surgical group to yield 84.7% power to detect a difference with an alpha = 0.05. In order to account for 10% missing data due to patient drop-outs and/or loss to follow-up, a total of 110 patients will be randomized and enrolled with 55 patients in each of the two surgical groups. The blocked randomization scheme will be designed for the potential enrollment of 60 patients in each of the two study groups.

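### A single block size of 10, stated in the protocol, with the surgeon drawing each assignment, leaves an expected one allocation in six predictable to anyone who has followed the sequence

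*Combined protocol and SAP*

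**What the plan says.** Under Interventions and Interactions, the Randomization paragraph states: "A blocked randomization scheme (block size of 10) will be used to assign study participants" to one of the two groups. It continues: "Prior to surgery, the surgeon will log on to the randomization website to determine each participant's surgical group assignment". The website records who logged on, the date and time, the patient and the assignment, and the operating room staff are then told the result.

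The Sample Size section gives the length of the sequence: "a total of 110 patients will be randomized and enrolled with 55 patients in each of the two surgical groups", and "The blocked randomization scheme will be designed for the potential enrollment of 60 patients in each of the two study groups". The Design and Setting lines describe one site. No stratification factor is named. The documents describe no blinding, no varying block size and no step that keeps the block size from the surgeon.

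Three other sections bear on the point. Under Informed Consent, the coordinator obtains consent in clinic after the patient has seen the surgeon. Under Physician assessments, the principal investigator completes the surgical documentation form for participants. Under Analytical Plan, the primary outcome is the patient-reported IKDC subjective score.

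**The concern.** A website hides the list, but it cannot hide an assignment that can be worked out by counting. Once five patients in a block have gone to one group, the rest of that block must go to the other. The block size is in the protocol and the surgeon sees each assignment as it is drawn, so the count is available to anyone who has followed the sequence.

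Foreknowledge could act in two ways: on which patients are offered the trial after seeing the surgeon, and on the order in which consented patients are logged on. If either led to patients with better prognosis entering one group, the imbalance would pass directly into the treatment difference. The outcome is patient-reported with no blinding described, and the Analytical Plan names no analysis model or baseline adjustment that might absorb part of the imbalance.

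**Working it through.** **Inputs.** From the protocol: block size 10; 110 patients, 55 per group; a list for 60 per group; one site. Assumed, because implied but not stated: 5:5 within each block and a single list.

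**The plan's own figures.** The plan gives no predictability figure. Its counts fit whole blocks: 110 / 10 = 11 and (2 × 60) / 10 = 12.

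**Certain assignments.** For a block of 2m with m per group, the expected number already determined is 2m / (m + 1). With m = 5 this is 10 / 6 = 1.67 per block, or 16.7%. Over 11 blocks it is 11 × 1.67 = 18.3 of 110. Enumerating all 252 balanced orders of a block agrees:

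| Certain assignments in a block | Share of blocks |
|---|---|
| 1 | 55.6% |
| 2 | 27.8% |
| 3 | 11.9% |
| 4 | 4.0% |
| 5 | 0.8% |

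At least one per block is always certain, so at least 11 of 110.

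**Best guess.** Always guessing the group that is behind in the block, and tossing a coin at ties, gives m + (2^(2m) / C(2m, m) − 1) / 2 correct. Here that is 5 + (1024 / 252 − 1) / 2 = 6.53 of 10, or 65.3%, against 50% under unrestricted randomization.

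**Alternatives.** The mixed schemes were simulated with a guesser who knows the set of sizes but not the size of the current block.

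| Scheme | Certain | Best guess right |
|---|---|---|
| Fixed 4 | 33.3% | 70.8% |
| Fixed 6 | 25.0% | 68.3% |
| Fixed 8 | 20.0% | 66.6% |
| Fixed 10 (the plan) | 16.7% | 65.3% |
| Random mix of 4, 6, 8 | about 2% | about 68% |
| Random mix of 8, 10, 12, 14 | about 0.7% | about 64.3% |

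**Illustration of bias (the steering is assumed).** Suppose patients whose assignment to one group was certain differ in prognosis by a gap g, in SD units, from those whose assignment to the other group was certain, always in the same direction, and that no other assignment is steered. One sixth of each group is affected, so the bias is g / 6. The rejection rates come from simulated trials with no true effect: 110 patients in 11 blocks of 10, two-sided 5% t-test.

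- g = 0.5: bias 0.5 / 6 = 0.083 SD; the test rejects about 7% of the time.
- g = 1.0: bias 1.0 / 6 = 0.167 SD; the test rejects about 13% of the time.

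**Power of a retrospective check.** About 18 flagged patients means about 9 per group. A two-sided 5% t-test with 9 per group has 17% power for a baseline gap of 0.5 SD and 51% for 1.0 SD.

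**The case against.** Several points on the other side stand.

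- **Knowledge of the sequence is assumed.** One in six applies to a person who knows every earlier assignment in the block. The number of surgeons is not given. That the principal investigator completes the surgical form suggests one person sees the sequence but does not establish it. The documents also do not say who sets the order of log-ons.
- **Consent comes first.** The coordinator consents patients in clinic and the assignment is drawn later. A queue of consented patients awaiting surgery weakens prediction at the time the trial is offered.
- **There are safeguards.** The website logs each draw, no study procedure precedes consent, cross-over patients are kept, and baseline IKDC is collected.
- **The gain is uneven.** The proposed mix removes nearly all certain assignments but improves the best guess by only about one percentage point.

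Four stronger readings are tempting, and the documents do not support them.

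- A reader might infer that selection took place. Nothing in the documents indicates it.
- A reader might infer that 10 is too small. Smaller fixed blocks are more predictable; the weakness is that the size is fixed and disclosed.
- A reader might infer that a modest 0.5 SD gap more than doubles the false-positive rate. That takes a gap of about 1.0 SD; at 0.5 SD the rate is about 7%.
- A reader might add the rule for changes of technique during surgery, "this patient will be recorded as a treatment cross-over as long as the patient continues to meet inclusion criteria", as a further route. By then the assignment is known under any block size, so varying the blocks would change nothing. Exclusion after randomization is a separate question.

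**Conclusion.** The concern holds as a design risk of moderate size that is cheap to reduce. With one list, 5:5 blocks and an observer who knows all earlier assignments, an expected 16.7% of assignments (about 18 of 110) are certain and 65.3% can be guessed correctly; both are lower if knowledge of the sequence is divided among surgeons. Any effect on the result depends on steering that is assumed here: a bias of about 0.08 SD with about 7% rejection at a 0.5 SD gap, and about 0.17 SD with about 13% at a 1.0 SD gap. The protocol's closing update says the sponsor has ended support and describes close-out visits, so the practical consequence may now be confined to how the results are read.

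**What to change.** **If enrolment is open or restarts.** In the Randomization paragraph, replace the stated block size with randomly varying sizes held by the statistician and disclosed neither in the protocol nor to the surgeon; a random mix of 8, 10, 12 and 14 is one example. Require consent and confirmed eligibility to be entered on the website before the assignment can be opened. The cost is one edited paragraph, one new list and one added website step. The statistical price is a possible imbalance of at most 7 rather than 5 if enrolment stops mid-block.

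**If enrolment has closed.** Use the stored log-on dates and times to rebuild the blocks and flag each assignment that was fully determined by the earlier ones. Compare baseline IKDC between groups among the flagged patients, and repeat the primary analysis without them as a sensitivity analysis. This needs no new data and only a few lines of code. State in the report that, with about 18 flagged patients at full enrolment and fewer if it stopped short, finding no baseline difference is not reassurance, and that assignments that were likely but not certain remain in the analysis.

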#### **Exclusion Criteria**

- Patients with a history of long term pain medication use and/or chronic pain conditions unrelated to the surgery.
- Subjects with severe renal disease, allergies to pain medication, and subjects that will have adverse drug-drug reactions from prescribed pain medication.
- Patients with previous reconstructive procedures, lateral retinacular release, or microfracture
- Active knee infection or sepsis at the time of surgery
- Meniscal injuries requiring repair
- Ligamentous instability
- Advanced degenerative or inflammatory arthritis
- Known cancer at the time of surgery
- Conditions that might interfere with recovery from knee arthroscopy (i.e. conditions or diseases of the nervous and/or muscular system, vascular disease, uncontrolled diabetes)
- Malignant tumor history or treatment of malignant tumor of the knee
- Lower extremity condition causing abnormal ambulation (e.g. ankle fusion, ankle arthroplasty, previous hip fracture, knee arthrofibrosis)
- Pregnant, breast feeding, or planning on becoming pregnant during the time frame of the study, (if a woman of child-bearing age)
- Emotional or neurological conditions that affect the subject's ability or willingness to participate in the study including mental illness or drug and/or alcohol abuse
- Severely overweight (BMI >40) at study enrollment or surgery
- Currently participating in another research study
- Prisoner or impending imprisonment
- Workers' Compensation claims

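### Does the cross-over rule allow patients to be dropped or re-counted after randomization in a way that favours single portal?

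*Combined protocol and SAP*

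**What the plan says.** The cross-over paragraph follows the Randomization text under Interventions and Interactions. For a patient assigned to single portal who is found in the operation to need two, it states that "this patient will be recorded as a treatment cross-over as long as the patient continues to meet inclusion criteria". It extends the rule to the other arm: "This will also be true for patients randomized to the two portal technique who undergo the single portal technique". It then adds: "Cross-over patients will not be excluded from the study". Few cross-overs are expected, but no rate is given.

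On timing, "Prior to surgery, the surgeon will log on to the randomization website", and the site keeps the allocation for each patient with the date and time. On recording, "The details of the surgical procedure for each study participant will be documented on the IKDC Surgical Documentation Form".

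Human Subjects Protection keeps participants in follow-up unless they ask to leave, seeks clinical data from those who do, and does not replace them. The Analytical Plan names the primary and secondary outcomes and the data handling. It names no analysis population.

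**The concern.** Two features look troubling together.

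First, the eligibility condition operates during surgery, when the surgeon already knows the allocation, and it is written only for patients who switch. Some exclusions could first come to light then, for example "Meniscal injuries requiring repair". A patient with that finding who keeps the assigned technique faces no matching check in this paragraph. Conversion out of surgical need is described only from single to two portals, so a rule that looks neutral could fall mostly on the single-portal arm.

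Second, keeping cross-overs in the study does not settle where they are counted. Counting them by technique received would move converters out of the single-portal group and into the two-portal group.

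If converters do worse, either practice would favour single portal, which is the direction of the hypothesis under Objectives.

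**Working it through.** **1. What the text requires**

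- *Direction.* The condition covers switches both ways, so the written rule does not differ by arm. Any imbalance would come from how often each kind of switch occurs.
- *Consequence.* The clause decides who is recorded as a cross-over. It says nothing about a switcher who fails the condition, and no section orders that patient's removal. The default in Human Subjects Protection is continued follow-up.
- *Which criteria.* The clause names inclusion criteria. These are age 21 to 65, willingness to comply, and a primary arthroscopy for meniscus or articular cartilage pathology. Of these, surgery could overturn only the pathology. The meniscal-repair item is an exclusion criterion, so it is reached only if inclusion criteria is read loosely to mean eligibility in general.
- *Criteria for everyone.* The exclusions tied to the time of surgery, such as "Active knee infection or sepsis at the time of surgery" and "Known cancer at the time of surgery", apply whichever technique is used.
- *Analysis group.* Cross-overs are retained, they are described by the arm to which they were randomized, and their allocation is stored. Nothing directs analysis by technique received.

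**2. Size if the text were misapplied**

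The documents give neither a conversion rate nor an outcome gap, so the inputs are assumed:

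- no true treatment effect;
- share *c* of single-portal patients converting (2%, 5%, 10%, which is 1.1, 2.75, 5.5 of 55);
- converters worse by *g* = 5 or 10 IKDC points;
- the same share of such knees, with the same gap, in the two-portal arm;
- no switching from two portals to one.

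If a fraction *f* of converters is dropped, bias = *cg* − *gc*(1 − *f*)/(1 − *cf*). With *c* = 0.10, *g* = 10, *f* = 0.5: 1 − 0.5/0.95 = 0.47.

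If all converters are counted as two-portal, bias = 2*cg*/(1 + *c*). With *c* = 0.10, *g* = 10: 2/1.1 = 1.82.

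| Bias towards single portal (points) | c = 2% | c = 5% | c = 10% |
|---|---|---|---|
| g = 10, one fifth dropped | 0.04 | 0.10 | 0.18 |
| g = 10, one half dropped | 0.10 | 0.24 | 0.47 |
| g = 10, by technique received | 0.39 | 0.95 | 1.82 |
| g = 5, one fifth dropped | 0.02 | 0.05 | 0.09 |
| g = 5, one half dropped | 0.05 | 0.12 | 0.24 |
| g = 5, by technique received | 0.20 | 0.48 | 0.91 |
| As randomized | 0 | 0 | 0 |

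Dropping one fifth of converters means 0.22, 0.55 or 1.1 patients of 55, so the first two cases are less than one person. For scale, Sample Size cites smallest detectable differences of 9.0 and 14.6. The largest dropping figure is 0.47/9.0, about 5% of the smaller. The largest figure by technique received is 1.82/9.0, about 20%.

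**3. Price of analysing as randomized**

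If each converter gets the full effect of the technique received, a true difference *D* shrinks by *cD*. For *D* = 9.0 this is 0.18, 0.45 or 0.90 points; for *D* = 14.6 it is 0.29, 0.73 or 1.46. Taking the stated 84.7% power with 50 per group at face value (two-sided, normal approximation), one-way conversion of 5% or 10% lowers it to 80.9% or 76.6%. The shrinkage runs towards no difference and cannot create an advantage for single portal.

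**The case for a change.** The best case for a change is that the silence is real and one sentence would end it. Keeping a patient is not the same as saying where that patient is counted. Analysis by technique received contradicts no sentence in the protocol. An unwritten rule can also be settled after outcomes are seen, in a trial whose surgeon knows the allocation. The sponsor's withdrawal of support, described in the Update to the study protocol, does not remove the need for a rule covering patients already randomized. If the trial ends smaller than planned, each converter weighs more.

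The silence stands: no section names the analysis group or says what becomes of a switcher who fails the condition. The claim that the text permits removal by arm does not stand. It needs an exclusion that is nowhere ordered, a loose reading of inclusion criteria, and conversion almost entirely in one direction. The larger figures all come from analysis by technique received, for which the protocol gives no positive support.

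A supportive per-protocol analysis built on the surgical form could not be endorsed either, because the appendix lists the IKDC questionnaires without showing which exclusions the form captures.

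**Conclusion.** No change follows. This is a gap that the analyst fills sensibly: in a randomized trial that retains cross-overs and logs their allocation, the ordinary primary comparison is by assigned group, and this bias is then zero. No stated rule or number produces a wrong result.

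Removal of some converters would matter little even if it happened, at 0.02 to 0.47 IKDC points over the assumed range. Counting them by technique received would matter more, at 0.20 to 1.82 points, but that would depart from normal practice and nothing in the protocol asks for it. These figures rest on assumed conversion of 2% to 10%, an assumed gap of 5 to 10 points, and no switching from two portals to one. The conclusion would differ if the protocol directed removal of ineligible switchers or analysis by technique received. It does neither.

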## **Outcome Measures**

### **Patient assessments:**

Patients will complete the patient-related IKDC questionnaires at each study visit except the one week visit. The IKDC is used to monitor knee symptoms, function, and activity level (1) The IKDC was developed and revised by knee experts as a knee-specific rather than a disease-specific evaluation. (1) A recent study by Van de Graff, et al demonstrated that the IKDC was better in all its measurement properties than the KOOS or the WOMAC for evaluating patients with meniscal injuries. (2)

At the pre-surgery visit, study participants will complete several components of the IKDC questionnaires including the demographic form, current health assessment form, and the subjective knee evaluation form. Patients will maintain a daily log to document their use of pain medications for the first two weeks after surgery. In addition, study participants will complete the subjective knee evaluation form at one month, three months, six months, and one year.

Patients will be contacted by phone on post-surgical days 1 and 4 to remind them to complete their daily log and to report their pain level and medication use. At each phone call and clinic visit, patients will be asked two questions: *1. What day did you feel that you had completed recovering from the surgery?* and *2. What day did you stop taking pain medicine?* Patients also will be asked these questions at the 30 day clinic visit.

If patients are unable or decline to return to clinic for follow-up, we will try to collect the patient-completed questionnaires either by telephone, by mail, or by a web-based link sent to them via a REDCap database survey at any study time point.

### **Physician assessments:**

The principal investigator will complete the IKDC knee history form, surgical documentation form and knee examination form at baseline. At 30 days, three months, six months, and one year the physician assistant or other designee will complete the knee examination form. Additionally, the rehabilitation duration will be noted at the 30 days and three month visit per patient report.

### **Patient Retention**

Every effort will be made to retain patients in the study to ensure complete data collection. During the study consent process, potential study participants will be educated regarding the importance of full participation in all visits. Study participants will be called at 1 day and 4 days after surgery. At these calls, patients also will be reminded of their upcoming appointments. Patients will also be reminded about their follow-up visits at all clinic visits. Patients will also be given an information packet about the study. This packet will include a list of the dates for the phone calls and the dates of their follow-up clinic visits.

If patients are unable or decline to return to clinic for follow-up, we will try to collect the patient-completed questionnaires either by telephone, by mail, or a web-based link sent to them via a REDCap database survey at any study time point.

